Safety consideration	
Time of Analysis
 
Given the fact that primary endpoint is prematurely determined in study treatment period, 2 types of analysis will be performed:
 
 • Primary criterion analysis • Final analysis 
Primary criterion analysis:
 
Primary criterion analysis will be performed once all patients included in efficacy set (70 evaluable patients) have completed 4 cycles of treatment or treatment discontinued prior to cycle 4 of the study and will consist of analyzing:
 
 • Primary criterion : MRD rate in bone marrow after the 4 cycles or at treatment discontinuation of GA-DHAP • Treatment exposure • Stem cell collection failure • Secondary safety endpoints 
Final analysis:
 
All analyses will be performed when all included patients will have performed the end of treatment visit (end of maintenance “on demand” period or treatment discontinued from the study).
 
 • AE of grade 3-5 (CTCAE – v 4.03) regardless the relationship to IMP occurring from the date of informed consent signature, and up to 28 days after last treatment administration, will be recorded on the AE pages of eCRF. • Some adverse events which are attributable to the ASCT procedure only and not to the study drug are not to be entered in the eCRF (listed in section 14.2). • Any grade for AESI will be collected from ICF signature and until 28 days after last treatment administration regardless the relationship to IMP • All events that meet one or more criteria of seriousness, regardless the relationship to IMP, occurring from the date of the informed consent signature, during treatment administration period and up to 28 days after last drug administration, will be reported as SAE.

	
A SAE that occurs after this time, including follow up period, will be reported if considered related to IMP.
 
In a case of SAE the Investigator must immediately (within 24 hours):
 
SEND the SAE pages to LYSARC Pharmacovigilance department: [contact] OR EMAIL TO [contact]
 
Pregnancy and suspected pregnancy will be reported on Pregnancy Form to LYSARC PV from the date of informed consent signature and up to 28 days after the last study drug administration.

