If the platelet count is $<50 \times 10^9 / L$, GA101 will not be administered and the platelet count will be closely monitored and platelet transfusion will be performed to maintain a platelet count $>20 \times 10^9 / L$.

If the patient presents an active infection of any grade at day 8 or at day 15 of the first cycle of induction treatment, GA101 will not be administered.

10.3.2 **Renal toxicity**

If $>50\%$ decrease of creatinin clearance, cisplatin will be stopped or replaced by carboplatinum AUC = 5

10.3.3 **Neurotoxicity**

In case of neurotoxicity such as peripheral neuropathy, severe constipation/paralytic ileus, ototoxicity: cisplatin should be reduced by 50% or stopped according to the discretion of the treating physician.

Carboplatinum AUC = 5 could be used instead of cisplatin

10.3.4 **Potential risk of Progressive Multifocal Leukoencephalopathy (PML)**

The therapy with anti-CD 20 antibodies (obinutuzumab) should be discontinued during the investigations of a potential PML and permanently stopped if the diagnosis of PML is confirmed. Discontinuation or reduction of any concomitant chemotherapy or immunosuppressive therapy should also be considered. The patient should be referred to a neurologist for the adequate monitoring and treatment of PML.

10.3.5 **Other toxicities**

Other toxicities will be managed according to local practice and guidelines of chemotherapy induced toxicities

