10.5 Prophylactic measures

10.5.1 **Infusion-Related Reactions related to Obinutuzumab**

The most frequently observed adverse drug reactions (ADR) in patients receiving Obinuzumab were IRR; these occurred predominantly during the first infusion. The incidence and severity of infusion related symptoms decreased substantially with subsequent infusion.

See also section 10.1.5. *Administration* for the management of IRR

During induction treatment, dexamethasone should be administrated before the infusion of Obinutuzumab

If a patient experiences an IRR during the prior infusion, he should receive 100mg prednisolone or equivalent.

If a patient does not experience an IRR (grade ≥ 1) during the first infusion, the premedication for the infusions of maintenance can be omitted.

The first Obinutuzumab infusion should be administered to patient after premedication with oral analgesic/anti pyretic (e.g. 1000mg) and anti-histaminic drug (e.g. 50 mg diphenhydramine)

Grade 4 (life-threatening)	Stop infusion and discontinue therapy.
Grade 3 (severe)	Temporarily interrupt infusion and treat symptoms. Upon resolution of symptoms, restart infusion at no more than half the previous rate (the rate being used at the time that the IRR occurred) and, if patient does not experience any IRR symptoms, infusion rate escalation may resume at the increments and intervals as appropriate for the treatment dose
Grade 1-2 (mild and moderate)	Reduce infusion rate and treat symptoms. Upon resolution of symptoms, continue infusion and, if patient does not experience any IRR symptoms, infusion rate escalation may resume at the increments and intervals as appropriate for the treatment dose

10.5.2 ***Tumor Lysis Syndrome***

Patients who are considered to be a risk of TLS (e.g. patients with a high tumor burden or a high circulating lymphocyte count) should receive adequate tumor lysis prophylaxis with allopurinol (or adequate alternative) and hydration starting 12-24 hours prior to the infusion of Obinutuzumab.

10.5.3 ***Infection***

Obinutuzumab should not be administrated in the presence of an active infection.

Prophylaxis of infections is required for all patients during all the study treatment, in the discretion of the treating physician.

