14.2 Adverse Events reporting rules

Due to expected toxicity of study treatment, all AEs of grade 3-5 for toxicities (hematological or non-hematological) (CTCAE – version 4.0) regardless relationship to investigational product occurring from the date of informed consent signature to 28 days after the last study drug administration of the study will be recorded in the AE pages of the eCRF. When associated to a SAE and regardless the time of occurrence and the grade, the AE must be reported as "Adverse Event" in the appropriate eCRF pages.

Whenever possible, symptoms should be grouped as a single syndrome or diagnosis. The investigator should specify the date of onset, intensity, action taken regarding trial medication, corrective therapy given, outcome of all AEs and his opinion as to whether the AE can be related to the study drugs.

All events that meet one or more criteria of seriousness (see Section 13.1.2.) will be reported as SAE (see Section 13.3).

General AE reporting rules:

- Non-serious AE will be reported through eCRF
- Any episode of any grade of toxicity, related to a SAE must be reported as "Adverse Event" in the appropriate eCRF pages regardless the time of occurrence
- Signs, symptoms and physical findings indicative of lymphoma or progression of lymphoma are not to be reported as "Adverse Event"
- "Alopecia" toxicity (any grade) will never be reported as "Adverse event"
- AEs will be considered ended (recovered without sequelae) when recovered to a grade 0 or baseline
- In case of screening failure, at least AEs corresponding to SAEs will be reported in the AEs pages of eCRF.
- When a medical history resolves or decreases at a grade lower than baseline, the new grade will be the new reference grade for following AEs
- For laboratory abnormalities, the laboratory test to be taken as reference will be the one performed nearest to the Cycle 1 Day 1.

Abnormal laboratory values reporting rules:

If a laboratory abnormality is one component of a diagnosis or syndrome (e.g., alkaline phosphatase and bilirubin 5 × ULN associated with cholecystitis), only the diagnosis (e.g., cholecystitis) or syndrome should be recorded on the AE page/screen of the eCRF. If the laboratory abnormality was not a part of diagnosis or syndrome, the laboratory abnormality should be recorded as an AE.

An abnormal laboratory value which is not a component of a diagnosis or syndrome is considered as an AE if the abnormality:

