### 3.2.3 Secondary safety endpoints

Summary of study drug administration including treatment duration and average dose will be displayed.

Number, frequency, reasons for premature treatment discontinuation and study discontinuation will be summarized.

Adverse events, clinical laboratory measurements will be described.

AEs will be classified using the latest version of Medical Dictionary for Drug Regulatory Activities (MedDRA) coding system at the time of database lock. The severity of the toxicities will be graded according to the National Cancer Institute (NCI) Common Terminology Criteria for Adverse Events (CTCAE) whenever possible. Subsets of AEs to be summarized include serious, NCI CTCAE grade severities, suspected treatment-related, and events that resulted in withdrawal of investigational product. The most severe grade of each preferred term for a patient will be utilized for summaries of adverse events by NCI CTCAE grade.

All AEs and SAEs will be described by system organ class and preferred term (a patient having the same event more than once will be counted only once) by period. Focus on AEs leading to death, AEs leading to discontinuation from treatment and AEs of special interest (i.e Tumor Lysis Syndrom) will also be displayed in a separate table and listing.

All deaths will be listed and summarized by cause of death and narratives of death will be also presented.

This endpoint will be performed on safety set (SS).

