**Listing 5.9-1 Patients with at least one dose interruption of GA101 – Safety set (XX patients)**

Patient identification number	Inclusion date	Number of cycles received	Adverse Event					
			Period	Description	Highest grade	Relationship with GA101	Action taken on GA101	Outcome
XXXXX	XX/XX/XXXX	XX	XX	XX	X	XX	XX	XX

Filter: Action taken on GA101 = Drug interrupted

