## 5.10 Safety analysis

### 5.10.1 Adverse Events

**Table 5.101-1 Summary of AEs – Safety set**

	Induction N=XX	ASCT N=XX	Maintenance N=XX	Total N=XX
Patients with at least one AE				
No	XX (XX.X%)	XX (XX.X%)	XX (XX.X%)	XX (XX.X%)
Yes	XX (XX.X%)	XX (XX.X%)	XX (XX.X%)	XX (XX.X%)
If yes, number of Aes by patients				
N	XX	XX	XX	XX
Missing	XX	XX	XX	XX
Mean (SD)	XX.X (XX.XX)	XX.X (XX.XX)	XX.X (XX.XX)	XX.X (XX.XX)
Median	XX.X	XX.X	XX.X	XX.X
Q1 ; Q3	XX ; XX	XX ; XX	XX ; XX	XX ; XX
Min ; Max	XX ; XX	XX ; XX	XX ; XX	XX ; XX
Patient with at least one AE of grade >= 3				
No	XX (XX.X%)	XX (XX.X%)	XX (XX.X%)	XX (XX.X%)
Yes	XX (XX.X%)	XX (XX.X%)	XX (XX.X%)	XX (XX.X%)
Patient with at least one fatal AE				
No	XX (XX.X%)	XX (XX.X%)	XX (XX.X%)	XX (XX.X%)
Yes	XX (XX.X%)	XX (XX.X%)	XX (XX.X%)	XX (XX.X%)
Patient with at least one AE leading to treatment discontinuation				
No	XX (XX.X%)	XX (XX.X%)	XX (XX.X%)	XX (XX.X%)
Yes	XX (XX.X%)	XX (XX.X%)	XX (XX.X%)	XX (XX.X%)
Patient with at least one AESI*				
No	XX (XX.X%)	XX (XX.X%)	XX (XX.X%)	XX (XX.X%)
Yes	XX (XX.X%)	XX (XX.X%)	XX (XX.X%)	XX (XX.X%)

\* AESI = Tumor Lysis Syndrom and IRR grade 4 occuring during or within 24 hours after the GA101 infusion.

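### Low-grade events that change obinutuzumab dosing need not reach the AE page, so the SAP's AE-based interruption and discontinuation outputs can undercount them

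*Protocol*

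**What the plan says.** **Collection.** Protocol 14.2 puts "all AEs of grade 3-5 for toxicities (hematological or non-hematological") on the AE pages, from consent to 28 days after the last study drug. The synopsis agrees: "AE of grade 3-5 (CTCAE – v 4.03) regardless the relationship to IMP". One stated exception is that "When associated to a SAE and regardless the time of occurrence and the grade, the AE must be reported". Others cover AESIs (14.5), certain laboratory abnormalities and the transplant period (both 14.2).

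**Dosing.** Section 10.3.1.2.3 has a dose not given in this case: "If the patient presents an active infection of any grade at day 8 or at day 15 of the first cycle". Section 10.5.3 is general: "Obinutuzumab should not be administrated in the presence of an active infection". Section 10.1.5 tells the site to stop or slow an infusion when a reaction develops, with no grade named. Section 13.1 lets the investigator discontinue treatment for toxicity, again with no grade.

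**Reporting.** SAP 3.2.3 names "events that resulted in withdrawal of investigational product" as an AE subset to summarise. In SAP 5.9.2, Table 5.9-6 counts patients with at least one obinutuzumab interruption. Listing 5.9-1, under the same title, carries "Filter: Action taken on GA101 = Drug interrupted". In SAP 5.10.1, Tables 5.101-1 and 5.101-2 count AEs, and related AEs, that led to discontinuation ("Patient with at least one AE leading to treatment discontinuation"), and Listing 5.10.1-2 lists the patients.

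**The concern.** The grade threshold at collection and the outputs at analysis do not match. A patient can miss a dose because of a grade 1 or 2 infection, exactly as the protocol requires, and have no AE row. An output that starts from AE rows cannot show that patient.

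Tolerability of obinutuzumab at induction and in the on-demand phase is a secondary objective, and AEs leading to withdrawal are a planned summary. This gap can only lower the AE-based counts. A reader would also take those counts as covering all grades: Table 5.101-1 has one row for any AE and another for grade 3 or higher, and Table 5.101-5 has rows for grades 1 and 2. Treatment can run for 3 years of maintenance and 3 more on demand, so minor infections are a plausible reason for missed doses.

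**Working it through.** The plan states no figure on this point, so there is none to reproduce. The check traces an event from the collection rule, through the dosing rule, to the output.

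**Step 1. Which grade 1-2 events must reach the AE page?**

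- Events linked to an SAE: yes, at any grade (14.2).
- AESIs: 14.5 lists tumour lysis syndrome and grade 4 infusion reactions. Reporting whatever the grade therefore adds only low-grade tumour lysis.
- Stand-alone laboratory abnormalities that require a change or interruption of the study drug: they count as AEs with no grade stated (14.2). Whether the grade 3-5 limit still applies to them is not said.
- Transplant period: new events related to obinutuzumab, no grade stated; new infections only from grade 3 (14.2).
- The line in 14.2 that non-serious AEs go through the eCRF states the route. It does not lift the threshold.

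What is left out is the non-serious, non-laboratory event of grade 1 or 2 outside the transplant period. No rule brings it in because it changed dosing.

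**Step 2. Do the dosing rules act on such events?**

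For infection, clearly: 10.3.1.2.3 applies at any grade and 10.5.3 has no grade limit. For infusion reactions, less uniformly: 10.1.5 says stop or slow without a grade, while the table in 10.5.1 gives rate reduction for grades 1-2 and temporary interruption for grade 3. Those two passages should be reconciled. The infection rules are enough for the point.

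**Step 3. What does each output show for such an event?**

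| SAP output | Source as printed | Result |
|---|---|---|
| Listing 5.9-1 | AE action field | Patient absent |
| Table 5.9-6 | Not stated | Absent if it uses the same filter |
| Tables 5.101-1, 5.101-2; Listing 5.10.1-2 | AE records | Discontinuation absent |
| Section 5.2.1, Table 4.7-1 | Discontinuation reason | Permanent stop present, with reason |
| Section 5.2.1, Listing 4.7-2 | Filter on discontinuation reason | Row present; AE columns may be blank |
| Table 5.9-3, by induction cycle | Doses given | Low or missing dose visible; no reason |
| Table 5.9-4, maintenance | Doses given | One total per patient; no reason |

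Two gaps remain. The AE-based discontinuation count can fall below the disposition count. And no output need show why a dose was temporarily omitted or interrupted for a low-grade event.

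**Step 4. Size.**

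Let N be the Safety Set, t the share of patients with an AE-driven interruption, and g the share of those whose only such events went unrecorded. The true count is N × t and the listing shows N × t × (1 − g). The documents give neither t nor g. As an illustration only, take N = 83, the planned enrolment:

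- t = 20%, g = 50%: true 83 × 0.20 = 16.6; listed 16.6 × 0.50 = 8.3, or 10% instead of 20%.
- Lowest of the assumed range (t = 10%, g = 75%): true 8.3; listed 8.3 × 0.25 = 2.1.
- Highest (t = 30%, g = 25%): true 24.9; listed 24.9 × 0.75 = 18.7.

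The relative loss is g itself, and g is unknown.

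**The case against.** The best defence is that the threshold is deliberate. Section 14.2 justifies it by the expected toxicity of the regimen. The trial has one arm, these summaries are descriptive, and the MRD primary endpoint is untouched. The IDMC triggers that state a grade (grade 3-4 infections, grade 4 infusion reactions) and the SAE trigger rest on events that are collected. All of that stands. It defends a threshold for general AE reporting. It does not defend a listing titled as all patients with a dose interruption but built from records that leave some of them out.

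The second defence is that other data cover the loss. Section 13.1 requires the circumstances of every premature discontinuation on its own CRF page, and SAP 5.2.1 tabulates them by reason, including adverse event. Dosing data show what was given on days 1, 8 and 15 of cycle 1. This largely answers the worry about permanent stops, apart from the mismatch between tables. For temporary omissions it answers only in part, because the dose tables carry no reason.

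A reader might go further and infer that every stop or skipped dose for a low-grade event is lost, that omitted day 8 and day 15 doses are invisible, or that the protocol orders a stop of treatment for infection. The documents support none of these. Stops are in disposition, omitted induction doses can be seen in Table 5.9-3, and the infection rules withhold a dose without ordering a permanent stop.

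A fair caution also remains: the eCRF is not among the documents, so it is not known whether the dosing page collects a reason for each omitted dose.

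**Conclusion.** The point holds in a limited form. Non-serious, non-laboratory events of grade 1 or 2 outside the transplant period need not be on the AE page even when they cause obinutuzumab to be withheld, interrupted or stopped. Listing 5.9-1, Tables 5.101-1 and 5.101-2 and Listing 5.10.1-2 can therefore undercount AE-driven interruptions and discontinuations; so can Table 5.9-6 if it shares the listing's filter. The discontinuation counts can also disagree with disposition Table 4.7-1.

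The direction is known and the size is not. The figures in the working rest on assumed rates and are no estimate. For permanent stops the gap can be measured at analysis by comparing the two counts on the same patients; Table 4.7-1 uses the Included Set and Table 5.101-1 the Safety Set. For temporary omissions it can be measured only if reasons were collected.

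The conclusion assumes that sites followed 14.2 as written. Sites that volunteered low-grade events would narrow the gap unevenly.

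**What to change.** 1. **SAP 5.9.2.** Derive Table 5.9-6 and Listing 5.9-1 from the drug administration records: planned dose not given, delayed or interrupted, with the reason where collected. Do not rely on the AE action field alone. State the source of Table 5.9-6.
2. **SAP 5.10.1.** Count a discontinuation with the reason adverse event in the AE-discontinuation summary even when no AE row exists. Reconcile it with Table 4.7-1 on the Safety Set. Footnote the AE collection threshold on every AE-based interruption and discontinuation output.
3. **Protocol 14.2, for data still to be collected.** Record an AE of any grade if it leads to omission, delay, interruption or discontinuation of obinutuzumab. This extends to clinical events what 14.2 already does for laboratory abnormalities. Say also whether the grade limit applies to the laboratory rule.

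The cost is some extra programming and a few extra AE entries. The SAP is dated late 2024 and the last visit is planned for Q1 2025, so items 1 and 2 matter most and item 3 reaches little of the data. Reasons for past temporary omissions may not be recoverable; if so, the footnote should say it. No dosing or other clinical rule changes.

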- results in discontinuation from the study; or
- requires treatment, modification/ interruption of IP dose, or any other therapeutic intervention; or
- is judged to be of significant clinical importance.

The investigator has to notify in the patient medical file all abnormal laboratory values considered as clinically significant (write next to each abnormal laboratory value assessed as clinically significant "CS" or precise it in the medical report).

Regardless of severity grade, only laboratory abnormalities that fulfill the seriousness criterion need to be documented as a serious adverse event.

During the transplant period (that is to say the period from the first day of hospitalization to the day before C1 Obinutuzumab maintenance), neutropenia and thrombocytopenia resulting from bone marrow aplasia will not be recorded as AEs in the eCRF. Only the following have to be recorded in the eCRF:

- any evolution of ongoing AE
- any new AE related, or that appears to be related, to Obinutuzumab
- any new infection from at least grade 3
- any new oral mucositis from at least grade 3
- any AE fulfilling seriousness criteria

A special attention is required for the following AEs:

- ICU admission whatever the cause
- Clinically Significant Neurological disorders
- Creatinin increased > 1.5 baseline

- Documented germ infection
- Prolongation of hospitalization beyond J 25 after stem cell reinfusion whatever the cause
- AE deemed unusual by the investigator

Please note that AEs of at least grade 3 associated with Stem Cell mobilization should be recorded in the eCRF

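### All-cause AE recording is restricted in the transplant period, yet SAP Table 5.101-1 and the pooled SOC/PT tables show those events beside or mixed with fully recorded ones, without a caveat

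*Protocol*

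**What the plan says.** **General rule.** Protocol section 14.2 requires "all AEs of grade 3-5 for toxicities (hematological or non-hematological", whatever the relationship to study drug, from consent to 28 days after the last administration. The synopsis (Safety consideration) has the same rule: "AE of grade 3-5 (CTCAE – v 4.03) regardless the relationship to IMP".

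**Transplant period.** Section 14.2 defines this as "the period from the first day of hospitalization to the day before C1 Obinutuzumab maintenance". Within it, "neutropenia and thrombocytopenia resulting from bone marrow aplasia will not be recorded as AEs in the eCRF". The section continues "Only the following have to be recorded in the eCRF" and names five categories:

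- any change in an ongoing AE
- new AEs that are, or appear to be, related to obinutuzumab
- new infections of grade 3 or more
- new oral mucositis of grade 3 or more
- anything serious

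A further list of events needing special attention follows, including creatinine rises, neurological disorders and ICU admission. The text does not say whether these are recorded when they fall outside the five categories.

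**Synopsis carve-out.** Some "adverse events which are attributable to the ASCT procedure only and not to the study drug are not to be entered" in the eCRF, with a pointer to section 14.2 for the list.

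**SAP.** Section 3.2.3 says AEs and SAEs will be described by SOC and PT, by period. Table 5.101-1 has columns for Induction, ASCT, Maintenance and Total. Its rows include any AE and "Patient with at least one AE of grade" 3 or higher. Its only footnote defines AESI. Tables 5.101-3 (SOC/PT) and 5.101-4 (SOC/PT by highest grade) have no period split.

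**The concern.** Table 5.101-1 invites the reader to compare columns that were collected under different rules. The transplant period contains the high-dose conditioning chemotherapy, and it could look safer than induction only because fewer kinds of event had to be entered. The pooled SOC/PT tables have the same weakness in a less visible form: a cytopenia rate there combines induction events, which are recorded, with aplasia events, which are barred. In a single-arm trial these tables are the main description of tolerability, so a reader needs to know which figures are complete.

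**Working it through.** The plan states no figure on this point, so there is none to reproduce. The check is a comparison of texts, followed by an illustration of direction and possible size.

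**1. What each text requires for a new event in the transplant period**

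| Event | Synopsis | Section 14.2, transplant rule |
|---|---|---|
| Aplasia neutropenia or thrombocytopenia | excludable if due to ASCT only | barred |
| Grade 3+ infection or oral mucositis due to ASCT only | excludable | required |
| Obinutuzumab-related AE | required at grade 3-5 | required, no grade floor |
| Serious or fatal AE | required | required |
| Other non-serious grade 3-4 AE, not obinutuzumab-related and not due to ASCT alone | required | not required |

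The scopes differ in both directions. Section 14.2 does not contain the list of procedure-attributable exclusions that the synopsis says is there.

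**2. Length of the period.** Maintenance starts 2 to 3 months after D1 of ASCT (section 10.2.3). If D1 means graft day and admission is on day -8, the period is 8 + 61 = 69 to 8 + 92 = 100 days. If D1 means the start of conditioning, it is about 61 to 92 days. Induction lasts 4 x 21 = 84 days. The two periods are of similar length, so the restricted period is not a short gap. Days do not measure events lost.

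**3. Direction and possible size for the grade 3 or higher row.** Let

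- t = share of patients with any grade 3 or higher AE in the transplant period
- c = share of those with at least one such event on the 14.2 list
- q = share with a recorded grade 3 or higher AE in another period, taken as independent

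If unlisted events are not entered:

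- ASCT column shortfall = t(1 - c)
- Total column shortfall = (1 - q) t (1 - c)

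Neither can be negative. The documents give no value for t, c or q, so these are assumptions:

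| | t = 0.5, c = 0.9 | t = 1.0, c = 0.3 |
|---|---|---|
| ASCT column | 0.5 x 0.1 = 5 points | 1.0 x 0.7 = 70 points |
| Total, q = 0.5 | 0.5 x 5 = 2.5 points | 0.5 x 70 = 35 points |
| Total, q = 0.9 | 0.1 x 5 = 0.5 points | 0.1 x 70 = 7 points |
| Total, q = 0.95 | 0.05 x 5 = 0.25 points | 0.05 x 70 = 3.5 points |

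The width of the range shows that the size is unknown. It also shows that the patient-level Total is protected when most patients already have a recorded severe AE elsewhere.

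**4. SOC/PT tables.** Event counts lose every unrecorded event. The patient rate for a given term is protected only where the same patient has the same term recorded in another period. In the highest-grade table, a patient whose worst episode fell in the transplant period can appear at a lower grade.

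**5. The any-AE row.** Obinutuzumab-related AEs and changes in ongoing AEs have no grade floor in the transplant period, whereas the general rule elsewhere starts at grade 3. This row can therefore be incomparable in either direction.

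**The case against.** The restriction is deliberate, and recording less around a transplant is reasonable. Several stronger readings are tempting, but the documents do not support them.

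- *The synopsis and 14.2 are rival rules.* The synopsis defers to 14.2, so an investigator who follows the pointer reaches one operative list. What remains is a mismatch in scope and wording.
- *The SAP presents the columns as complete.* It makes no such claim, and it gives ASCT its own column. What it lacks is a statement of the rule.
- *Every unlisted grade 3-4 event is lost.* The text says what has to be recorded; only aplasia neutropenia and thrombocytopenia are expressly barred. Sites may have entered more, particularly from the special-attention list.
- *Safety is understated throughout.* SAEs, fatal AEs, obinutuzumab-related AEs, and grade 3 or higher infection and oral mucositis are required in full. AESI are reportable at any time under section 14.5. The section 12 IDMC triggers for transplant toxic deaths and for SAEs are unaffected.
- *The rates cannot be compared with other trials.* That depends on those trials' collection rules, which are not in the documents.

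It can also be said that SAP 3.2.3 already plans SOC/PT by period. That is correct, and it means the pooled shells depart from the SAP's own text. Finally, taking the transplant period out of the only headline totals would remove severe events that were recorded. That objection stands, and the fix below respects it.

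**Conclusion.** The point holds in limited form. The all-cause grade 3 or higher rate in the ASCT column and the pooled SOC/PT rates, most clearly for cytopenias, are understated against the general recording rule and are not comparable with induction or maintenance. The direction follows from the texts. The amount cannot be derived from them, and the 5 to 70 points above rest wholly on assumed inputs and on unlisted events not being entered. The patient-level Total may be little affected. The primary endpoint is not touched. The change should be made because, without a caveat, a recording rule can be read as a safety result.

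**What to change.** 1. **Protocol.** Align the synopsis carve-out with section 14.2 so that both describe the same list, and state whether special-attention events outside the five categories are recorded. On the planned dates (last inclusion September 2018) the transplant data are already collected, so this mainly documents what was done.
2. **SOC/PT and grade tables.** Produce Tables 5.101-3 and 5.101-4 by period, as SAP 3.2.3 states. Onset period is already a planned variable in Table 5.101-5.
3. **Table 5.101-1.** Keep the existing Total and add a second Total without the transplant period. Footnote the ASCT and both Total columns with the 14.2 rule.
4. **Cross-period comparison.** Use only categories collected alike in every period: SAEs, fatal AEs, AESI, grade 3 or higher obinutuzumab-related AEs, grade 3 or higher infection, and grade 3 or higher oral mucositis. The grade limit on related AEs is needed because the transplant rule sets no floor for them.

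The cost is some protocol wording, a few more tables and a less simple Total. No new data are needed. The SAP changes should be made before database lock, which is when SAP section 1 says the plan is final.
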